examine *retrospective* changes in sleep. These include examining changes in subjective measures of sleep quality that are captured in the BSWSQ, ISI, and FOSQ-10 questionnaires. Changes on these questionnaires will be examined with repeated measure ANOVA. Another exploratory measure to be analyzed in the same manner will be a change in depressive symptom severity as captured on the CES-D. A final exploratory measure will be to examine the change in the number of caffeinated beverages during work shifts. Given that there is tremendous variability in the caffeine content of caffeinated beverages, within subject changes will be examined with multilevel modeling.

Power/Sample Size:

For estimation of sample size, we have reduced our aim to the single, most important outcome measure - will sleep efficiency improve in the drug condition - and reduced the statistical testing to a *t*-test. In previously published work (20), a variance of 3.62% - 3.87% was observed following use of 10 mg of suvorexant or placebo. For purposes of this sample size estimation, we can estimate $\sigma = 5.55\%$ (average variance * 150%, with the increase due to our use of actigraphy instead of polysomnography as a reporter). Setting $\alpha = 0.05$ and power = 80%, we would be able to detect a difference of 5.2% in sleep efficiency (i.e., that which was observed in a previous trial of 10 mg suvorexant in those with insomnia (21)) with 19 participants in each group (n=38 total).

**PROTOCOL
 APPLICATION FORM
 Human Subjects Research
 Stanford University**

Title : A double-blind, placebo-controlled, randomized, parallel design study to examine the effectiveness of 10 mg suvorexant in improving daytime sleep in shift workers

Approval Period: Draft

Protocol Director				
Name [name]		Degree (Program/year if student) PhD		Position, e.g. Assistant Professor, Resident, etc. Asst Professor
Department Psych/Sleep Medicine	Mail Code 5550	Phone [REDACTED]	Fax	E-mail [contact]
CITI Training current				Y

Admin Contact				
Name [name]		Degree (Program/year if student) BS		Position, e.g. Assistant Professor, Resident, etc.
Department Psychiatry and Behavioral Sciences	Mail Code 5550	Phone [REDACTED]	Fax	E-mail [contact]
CITI Training current				Y

Investigator				
Name		Degree (Program/year if student)		Position, e.g. Assistant Professor, Resident, etc.
Department	Mail Code	Phone	Fax	E-mail
CITI Training current				

Other Contact				

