Baseline visit (3 hours): Consent process followed by baseline assessments using questionnaires, blood draw, urinalysis, electrocardiogram, and physical exam

Week 1-2: Sleep will be monitored with a wrist-worn device that monitors movement as well as participant-completed logs. No changes in behavior.

Weeks 3-5: Sleep will be continued to monitored as during baseline. Subjects will also take a pill 30 minutes prior to day time sleep attempts. This pill will have either drug or placebo (randomized)

End of study visit (2 hour): Same procedures as baseline visit.

- b) Explain how the above research procedures are the least risky that can be performed consistent with sound research design.**

All procedures in this study were designed with the goal of minimizing exposure to risk balanced with gaining a greater understanding of whether this treatment would help the individuals who participate in this study and for whom there is no currently available FDA-approved therapy.

- c) State if deception will be used. If so, provide the rationale and describe debriefing procedures. Since you will not be fully informing the participant in your consent process and form, complete an alteration of consent (in section 13). Submit a debriefing script (in section 16).**

Deception will not be used.

- d) State if audio or video recording will occur. Describe what will become of the recording after use, e.g., shown at scientific meetings, erased. Describe the final disposition of the recordings.**

Audio and video recordings will not occur.

- e) Describe alternative procedures or courses of treatment, if any, that might be advantageous to the participant. Describe potential risks and benefits associated with these. Any standard treatment that is being withheld must be disclosed in the consent process and form. (i.e. standard-of-care drug, different interventional procedure, no procedure or treatment, palliative care, other research studies).**

Instead of participating, individuals who work night shifts can use any one of a number of behaviors or medications to help them sleep during the day time. None of the available pharmacotherapies induce natural sleep and the behavioral therapies have efficacy in only a subset of individuals.

- f) Will it be possible to continue the more (most) appropriate therapy for the participant(s) after the conclusion of the study?**

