The risks of the Radioisotopes/radiation-producing machines (e.g., X-rays, CT scans, fluoroscopy) and associated risks.

None

The risks of the Physical well-being.

The wrist worn activity monitors may cause a rash (contact dermatitis) on the wrist underneath where the device makes contact with the skin. This risk is similar to wearing a wrist watch. If this occurs, we will recommend that participants move the watch and use skin cream on the rash.

The risks of the Psychological well-being.

There is a possibility of increased depressive symptoms following use of this medication. We will monitor this at the end of the first week of drug use. There is always a risk when completing questionnaires that participants will learn something about themselves that negatively affects their psychological well-being.

The risks of the Economic well-being.

Title : A double-blind, placebo-controlled, randomized, parallel design study to examine the effectiveness of 10 mg suvorexant in improving daytime sleep in shift workers

Approval Period: Draft

There is no likely risk to economic well-being.

The risks of the Social well-being.

There is no likely risk to social well-being.

Overall evaluation of Risk.

Low - innocuous procedures such as phlebotomy, urine or stool collection, no therapeutic agent, or safe therapeutic agent such as the use of an FDA approved drug or device.

- b) If you are conducting international research, describe the qualifications/preparations that enable you to both estimate and minimize risks to participants. Provide an explanation as to why the research must be completed at this location and complete the [LINKFORINTERNATIONALRESEARCHFORM] International Research Form. If not applicable, enter N/A.**

n/a

- c) Describe the planned procedures for protecting against and minimizing all potential risks. Include the means for monitoring to detect hazards to the participant (and/or to a potential fetus if applicable). Include steps to minimize risks to the confidentiality of identifiable information.**

Two weeks after initiating the baseline portion of the study, participants will return to the lab and be monitored for risk exposure. One week after initiating medication, subjects will again return to the lab and be monitored for risk exposure.

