- d) Explain the point at which the experiment will terminate. If appropriate, include the standards for the termination of the participation of the individual participant Also discuss plans for ensuring necessary medical or professional intervention in the event of adverse effects to the participants.**

The experiment will terminate at the end of the three weeks of drug administration. In case of an adverse event during the protocol, Drs. [name] and [name] will be able to advise a proper course of action.

- e) Data Safety and Monitoring Plan (DSMP). See guidance on Data Safety and Monitoring.**

A Data and Safety Monitoring Plan (DSMP) is required for studies that present Medium or High risk to participants. (See Overall Evaluation of Risk above). If Low Risk, a DSMP may not be necessary. Multi-site Phase III clinical trials funded by NIH require the DSM Plan to have a Data Safety Monitoring Board or Committee (DSMC or DSMB). The FDA recommends that all multi-site clinical trials that involve interventions that have potential for greater than minimal risk to study participants also have a DSMB or DSMC.

The role of the DSMC or DSMB is to ensure the safety of participants by analyzing pooled data from all sites, and to oversee the validity and integrity of the data. Depending on the degree of risk and the complexity of the protocol, monitoring may be performed by an independent committee, a board (DSMC/DSMB), a sponsor's Data Safety Committee (DSC), a Medical Monitor, a sponsor's safety officer, or by the Protocol Director (PD).

Describe the following:

What type of data and/or events will be reviewed under the monitoring plan, e.g. adverse events, protocol deviations, aggregate data?

Adverse events, consent forms, and protocol deviations will be monitored.

Identify who will be responsible for Data and Safety Monitoring for this study, e.g. Stanford Cancer Institute DSMC, an independent monitoring committee, the sponsor, Stanford investigators independent of the study, the PD, or other person(s).

The PD in collaboration with Drs. [name] and [name] will be the responsible entity.

Provide the scope and composition of the monitoring board, committee, or safety monitor, e.g., information about each member's relevant experience or area of expertise. If the Monitor is the

Title : A double-blind, placebo-controlled, randomized, parallel design study to examine the effectiveness of 10 mg suvorexant in improving daytime sleep in shift workers

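### Depressive worsening is a named drug risk, but the only stated by-arm analysis is a comparison of CES-D means, which at 19 per arm is unlikely to show a few large individual worsenings

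*Combined protocol and SAP*

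**What the plan says.** **The risk.** Section 9(a) of the protocol application, under psychological well-being, states: "There is a possibility of increased depressive symptoms following use of this medication". It continues: "We will monitor this at the end of the first week of drug use". Section 9(c) describes the matching visit: "One week after initiating medication, subjects will again return to the lab and be monitored for risk exposure". Neither place names an instrument or says how the result will be summarised.

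**The analysis.** Section 2.7, under exploratory measures, takes the shift-work, insomnia and functional-outcome questionnaires first: "Changes on these questionnaires will be examined with repeated measure ANOVA". It then adds: "Another exploratory measure to be analyzed in the same manner will be a change in depressive symptom severity as captured on the CES-D". It gives no CES-D time points or model terms, and no worsening threshold, count, listing or shift table.

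**The schedule.** Section 2(a) includes questionnaires, not named individually, in the baseline visit and then says: "End of study visit (2 hour): Same procedures as baseline visit". Section 9(d) sets the end of the study: "The experiment will terminate at the end of the three weeks of drug administration". The CES-D form is among the attachments in section 16.

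**Other oversight.** Section 9(e) has adverse events and protocol deviations monitored by the Protocol Director together with two board-certified sleep physicians. It makes any SAE or SUSAR a trigger for ending the study.

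**The concern.** The plan anticipates a specific harm and then analyses it with the tool it uses for efficacy scales. A comparison of means asks whether the typical participant changed. A drug risk of this kind may instead show as large worsening in a few people while most are unchanged. If the drug also helps sleep, as the trial hypothesises, some of the others may feel slightly better, which pulls the arm mean back towards zero.

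The stake is what the trial can report. A null CES-D result could be read as showing no effect on depressive symptoms when a few participants on drug had worsened substantially, and the plan contains no other by-arm summary that would show this.

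**Working it through.** **Inputs from the documents.** 19 participants per arm, 38 in total, alpha 0.05 and 80% power (section 2.7); three weeks of drug (section 9(d)). The documents give no CES-D standard deviation, worsening size or worsening rate, so every CES-D value below is an assumption and is shown over a range.

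**1. The plan's own figure.** The sample size is set on sleep efficiency, with a difference of 5.2 and an SD of 5.55. Noncentrality = 5.2 / (5.55 × √(2/19)) = 2.89 on 36 degrees of freedom. The two-sided t-test then has 80.2% power, so 19 per arm is reproduced. There is no corresponding figure for the CES-D.

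**2. Can small improvements cancel a few worsenings?** If k of n = 19 worsen by w points and the rest improve by i, the arm mean change is (k·w − (n − k)·i)/n.

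- 2 worsen by 16, 17 improve by 2: (32 − 34)/19 = −0.11, with 2/19 = 11% clearly worse.
- 3 worsen by 12, 16 improve by 2: (36 − 32)/19 = +0.21, with 3/19 = 16% clearly worse.

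The improvement in each remaining participant that brings the mean to exactly zero is k·w/(n − k):

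| Number worsening | by 10 points | by 15 | by 20 |
|---|---|---|---|
| 1 | 0.56 | 0.83 | 1.11 |
| 2 | 1.18 | 1.76 | 2.35 |
| 3 | 1.88 | 2.81 | 3.75 |

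**3. How often would the comparison of means show harm?** 20,000 simulated trials per row and SD; two-sided t-test at 0.05 on change scores, which equals the group-by-time test with two time points; placebo mean change 0; SD of change 4, 6 or 8 around the stated mean change.

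| Drug arm | True mean difference | Significant for harm (SD 4 / 6 / 8) |
|---|---|---|
| 2 worsen by 15, others 0 | 1.58 | 8.5% / 7.4% / 6.2% |
| 3 worsen by 15, others 0 | 2.37 | 16.2% / 11.9% / 9.6% |
| 3 worsen by 20, others 0 | 3.16 | 18.7% / 14.9% / 12.4% |
| 2 worsen by 15, others improve by 2 | −0.21 | 0.2% / 0.8% / 1.2% |
| 3 worsen by 15, others improve by 2 | 0.68 | 0.8% / 1.9% / 2.3% |

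The first three rows have no offset at all, and detection is already below 20%. The small sample is the main cause; cancellation makes it worse.

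**4. What would counts add?** A between-arm test on counts would also be weak: Fisher exact p is 0.49 for 2 against 0, 0.23 for 3 against 0, 0.11 for 4 against 0 and 0.046 for 5 against 0. The value lies in visibility. The chance of at least one case in 19 is 1 − (1 − r)^19, which is 62% at r = 5% and 86% at r = 10%. Exact 95% intervals are 1.3% to 33.1% for 2/19 and 3.4% to 39.6% for 3/19. Seeing 0/19 excludes only rates above 1 − 0.05^(1/19) = 14.6% (one-sided 95%).

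**The case against.** The strongest reply is that the ANOVA is not offered as the safety safeguard. Individuals are watched by another route: the check at the end of drug week 1, the lab visit in section 9(c), adverse event review with two physicians, and the SAE/SUSAR trigger. A null group mean does not switch any of these off. That stands. A reader might infer that a serious case would go unnoticed, and the documents do not support it. What this route lacks is a stated instrument for the week-1 check and a pre-stated summary by arm.

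A reader might also infer that the CES-D is given only at baseline and end of study, so that the week-1 check feeds no analysis. The text does not establish this. Section 2(a) is a summary and leaves out visits that section 9(c) describes. Section 2.7 gives no CES-D time points, and the CES-D may be the week-1 instrument. The supportable criticism is that the visible text does not say.

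Finally, the table would be imprecise at this sample size and the study is rated low risk. The imprecision is real, and it is why the proposal is descriptive and carries no test.

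**Conclusion.** The point holds as a low-cost improvement to the reporting of a harm the protocol names. The one stated by-arm analysis of depressive symptoms would show two or three worsenings of 15 points as significant harm in about 6% to 16% of trials without any offset, and in about 0.2% to 2.3% if the others improve by 2 points. These rates rest on the assumed CES-D values and on reading the ANOVA as a comparison of change between arms, since its terms are not spelled out.

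It would go too far to say that better sleep *would* cancel the worsenings. The documents give no size for either effect, so they support only that it *could*. No planned efficacy test or primary conclusion is affected.

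**What to change.** 1. Name the CES-D as the instrument at the existing drug-week-1 visit, and state all its time points in section 2.7.
2. Add to section 2.7 a descriptive safety table by arm, giving each participant's largest CES-D increase from pre-treatment at week 1 or end of study (this needs no threshold), and the number and percentage at or above a threshold fixed before unblinding. Give an exact confidence interval and no hypothesis test.
3. Keep the repeated-measures ANOVA as the exploratory mood outcome.

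The cost is at most one extra self-completed form per participant and one extra table. The intervals will be wide, as shown above, and the report should say that few or no cases does not establish absence of risk. The threshold here is for reporting only; any clinical action level is for the investigators to define.

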After conclusion of the study, participants would be able to contact their physicians to obtain a prescription for the medication used in this study.

- g) Study Endpoint. What are the guidelines or end points by which you can evaluate the different treatments (i.e. study drug, device, procedure) during the study? If one proves to be clearly more effective than another (or others) during the course of a study, will the study be terminated before the projected total participant population has been enrolled? When will the study end if no important differences are detected?**

The primary endpoint of this study is a change in total sleep time during day time sleep episodes. Given the blinding of the study and the relatively small population being studied, we do not intend to examine the primary outcome prior to study completion (38 total subjects).

3. Background

- a) Describe past experimental and/or clinical findings leading to the formulation of the study.**

The hypocretins (orexins) are a pair of neuropeptides produced by a small group of hypothalamic neurons

Title : A double-blind, placebo-controlled, randomized, parallel design study to examine the effectiveness of 10 mg suvorexant in improving daytime sleep in shift workers
Approval Period: Draft

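### Minor: the planning SD of 5.55% does not follow from its printed inputs and rule, which give 5.62%; exact t-test power at 19 per group is then 79.3%, not 80.2%.

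*Combined protocol and SAP*

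**What the plan says.** The Power/Sample Size paragraph of section 2.7 is the only power calculation in the documents. It works with sleep efficiency alone and says that the authors have "reduced the statistical testing to a *t*-test".

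- **Inputs for the spread.** From a cited earlier study (reference 20), "a variance of 3.62% - 3.87% was observed following use of 10 mg of suvorexant or placebo".
- **Rule and result.** Sigma is set at 5.55%, and the rule is given in brackets as "average variance * 150%, with the increase due to our use of actigraphy instead of polysomnography as a reporter".
- **Error rates.** "Setting $\alpha = 0.05$ and power = 80"%. Whether the test is one- or two-sided is not stated.
- **Conclusion.** "we would be able to detect a difference of 5.2% in sleep efficiency" "with 19 participants in each group (n=38 total").

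The paragraph does not show how the average was taken, and no other section gives further variability figures.

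**The concern.** The paragraph prints its inputs, its rule and its result together, so a reader can redo the step from one to the next, and it does not come out. The stated sigma is smaller than the one that the rule produces, which is the favourable direction for power. The calculation also has almost no slack: at the printed sigma, 19 per group clears 80% by only 0.2 points, so a small change in sigma takes the stated design below its own target.

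There is a wording problem in the same sentence. The inputs are called a variance, but 1.5 times their average is then used as sigma, an SD. A reader therefore has to infer both the averaging and the quantity being averaged.

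What is at stake is whether the planning SD and the power quoted from it can be rebuilt from the page. The size of the trial is not in question.

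**Working it through.** **Inputs**, all from the Power/Sample Size paragraph of section 2.7: published values 3.62 and 3.87; multiplier 1.5; printed sigma 5.55; difference 5.2 percentage points; alpha 0.05; power 80%; 19 per group. Two-sided testing is my assumption, supported by step 1.

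**1. Reproduce the plan's figure.** For a two-sample t-test with n per group, the noncentrality is δ / (σ√(2/n)) on 2n − 2 degrees of freedom. Power is the probability that a noncentral t variable exceeds the two-sided 5% critical value.

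With δ = 5.2, σ = 5.55 and n = 19: noncentrality = 5.2 / (5.55 × √(2/19)) = 2.888 on 36 df, and power = 80.2%. At 18 per group it is 78.0%. The smallest n is therefore 19, as stated.

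With the same σ, the normal approximation n = 2σ²(1.960 + 0.842)² / δ² gives 17.9, so 18 per group, and a one-sided exact t-test needs 15. Given 5.55 as the SD, the two-sided exact t-test is the variant that yields 19.

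**2. Apply the printed rule to the printed inputs.**

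- Arithmetic mean: (3.62 + 3.87) / 2 = 3.745; × 1.5 = 5.6175, or 5.62%.
- Geometric mean × 1.5 = 5.614; harmonic 5.611; root-mean-square 5.621.

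No standard average of the two values gives 5.55.

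**3. What would give 5.55?** 5.55 / 1.5 = 3.70 exactly. That is 3.745 rounded to one decimal before multiplying. A weighted average would need (3.87 − 3.70) / (3.87 − 3.62) = 68% of the weight on 3.62. Keeping 3.745 would need a multiplier of 5.55 / 3.745 = 148.2%.

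**4. Consequence of the corrected sigma** (two-sided, alpha 0.05, difference 5.2 points):

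| SD used | Source | Exact t power, 19 per group | Smallest n per group, exact t | Normal-approximation power, 19 per group |
|---|---|---|---|---|
| 5.43 | 1.5 × 3.62 | 81.9% | 19 | 83.9% |
| 5.55 | as printed | 80.2% | 19 | 82.3% |
| 5.6175 | 1.5 × 3.745 | 79.3% | 20 (81.4%) | 81.4% |
| 5.805 | 1.5 × 3.87 | 76.6% | 21 | 78.8% |

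At 5.6175 and 19 per group, the difference detectable with 80% power by the exact t-test is 5.25 points.

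**5. Variance or SD?** If the inputs were true variances, sigma would be √(1.5 × 3.745) = 2.37 or 1.5 × √3.745 = 2.90. The exact t-test would then need 5 or 7 per group. Neither is near 19, so the calculation treats the inputs as SDs.

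**The case against.** **The average may not be the midpoint.** The plan gives a span and says only that an average was taken. If the cited study reported several values, or if one arm carried more weight, 3.70 could be a proper average; 2:1 weighting towards 3.62 gives 3.703, and × 1.5 = 5.555. This stands as a possibility, and the fix is conditional on it. But the sentence ties the values to suvorexant or placebo, so two values is the natural reading, and nothing printed supports a weighting.

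**It is only rounding.** Probably so. But the inputs and sigma are all printed to two decimals, no rounding step is stated, and the rounding is what puts the power above 80%.

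**It is immaterial.** Largely true. The gap in sigma is 5.6175 − 5.55 = 0.07 points, about 1.2%, within a figure already raised by a judgemental 50%. The 0.9-point change in power is much smaller than the range from 81.9% to 76.6% across the two inputs. The effect is printed to one decimal, and with sigma at 5.6175, true differences of 5.15 and 5.25 give about 78.5% and 80.0%. Rounding of the effect alone therefore matters about as much. This fixes the grade at minor; it does not make the printed step correct.

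**A stronger reading that the documents do not support.** A reader might infer that the stated 19 can arise only from 5.55 used as an SD in an exact t-test. It cannot be put that way: 5.43 also gives 19 by the exact t-test, and 5.62 gives 19 by the normal approximation (18.3, rounded up).

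**Conclusion.** The printed sigma does not follow from the inputs and rule beside it: they give 5.62%, and 5.55% corresponds to an average of 3.70. Early rounding is the likeliest explanation, but the documents cannot settle it. By the two-sided exact t-test, power at 19 per group falls from 80.2% to 79.3%, and the n for 80% rises from 19 to 20 per group. By the normal approximation 19 is still enough. This is a minor correction.

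It rests on three assumptions: the two printed values are the ones averaged, they are SDs despite their label, and the test is two-sided.

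A reader might go further and infer that the trial is underpowered or should enrol more. The figures do not support that: the shortfall is under one point and depends on which formula is used. Nor does the point say anything about power for total sleep time, which section 2(g) of the protocol application names as the primary endpoint, or for the multilevel model in section 2.7. The calculation covers neither.

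**What to change.** Unless the source values support 5.55%, in which case the averaging should be shown, restate sigma as 5.62%. Replace the conclusion with a line to this effect: *with 19 per group, power is about 79% for a 5.2-point difference in sleep efficiency (80% for 5.25 points), two-sided exact t-test*. After checking reference 20, call the 3.62 and 3.87 figures SDs instead of variances. Keep 38 participants.

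The cost is a reworded sentence or two in section 2.7, with no change to enrolment, conduct or analysis. The downside is that the stated power falls by about one point, to just under the nominal 80% by the exact t-test.
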